### 7.2 WU PI Reporting Requirements

The study principal investigator and study coordinator will monitor for breaches of confidentiality and other adverse events on an ongoing basis. Once the PI or study coordinator becomes aware of a reportable adverse event, the event will be reported to HRPO according to institutional guidelines.

Protocol and/or consent revisions will be submitted to HRPO and approved prior to being implemented.

Pre-approval of all protocol exceptions must be obtained prior to implementing the change.

## 8.0 Data Collection and Security

The names of patients enrolled in the study will be recorded on an enrollment log that will include the participant's name and an assigned study ID. Additional data from the patient's medical record will be collected, such as age, sex, comorbidities, etc.

The handheld ketone meter (Keto-Mojo) readings will be automatically uploaded to a secure, HIPAA-compliant cloud platform monitored by the study team.

Study data will be stored and analyzed on a password protected, encrypted device. Only approved study personnel will have access to subject information. No subject PHI will be shared outside of the approved study personnel

## 9.0 Data Safety and Monitoring

The study Principal Investigator and Research Patient Coordinator will monitor for any safety concerns on an ongoing basis. Any symptomatic hypotension, electrolyte disturbance, or weight loss exceeding 10% of baseline will prompt protocol review and dietary adjustment by the study team. Should the principal investigator or designee become aware of any breach of confidentiality, or adverse event, the event will be reported according to institutional guidelines as outlined above, in Section 7.0

## 10.0 Statistical Considerations

All analyses will follow an intent-to-treat principle. Continuous variables will be summarized as mean  $\pm$  standard deviation, with within-subject changes analyzed using repeated-measures mixed-effects models. Dichotomous outcomes will be reported as proportions with 95% confidence intervals. The feasibility benchmark for success will be defined as at least 80% participant retention and 70% adherence to target ketosis levels across the study period

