## 1.0 Synopsis

Title:	Nutritional Ketosis as a Novel Therapeutic Strategy to Stabilize Chronic Aortic Dissection in Marfan Syndrome
Study Description:	Patients with Marfan syndrome who have chronic or residual aortic dissection remain at ongoing risk for progressive aortic dilation and eventual need for operative repair. Despite advances in antihypertensive therapy and open/endovascular/hybrid techniques, no medical therapy has been shown to slow aortic enlargement once chronic dissection is established. But promising results have been demonstrated in rodent studies utilizing ketogenic dietary interventions. Therefore, this prospective, single-arm, intent-to-treat pilot clinical trial will test the feasibility, safety, and potential efficacy of inducing and maintaining nutritional ketosis in patients with Marfan syndrome and chronic aortic dissection
Objectives:	
Primary Objective:
 
 
To test the feasibility, safety, and potential efficacy of inducing and maintaining nutritional ketosis in patients with Marfan syndrome and chronic aortic dissection (Prior type A dissection with residual distal dissection or Stanford Type B; and a maximal aortic diameter 4.0-5.0 cm).
 
 
Secondary Objective:
 
 
Observation of changes related to aortic dissection and inflammatory markers
 
Patient adherence to ketogenic dietary recommendations
 

Endpoints:	
Primary Endpoint:
 
 
Freedom from aortic intervention at 12 months compared with historical controls.
 
 
Secondary Endpoints:
 
 
Change in aortic diameter
 
Growth rate
 
Systemic inflammatory markers
 
Dietary adherence metrics
 

Study Population:	15 patients- Prospective Cohort 15 patients- Historical Control
Phase:	N/A
Description of Sites / Facilities Enrolling:	Washington University School of Medicine / Barnes-Jewish Hospital

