### 3.0 Objectives and Endpoints

Objectives	Endpoints
Primary	
Test the feasibility, safety, and potential efficacy of inducing and maintaining nutritional ketosis in patients with Marfan syndrome and chronic aortic dissection	Freedom from aortic intervention at 12 months compared with historical controls.
Secondary	
Observation of changes related to aortic dissection and inflammatory markers  Patient adherence to ketogenic dietary recommendations  Explore the mechanistic relationship between circulating ketone levels, systemic inflammation, and aortic remodeling as measured by imaging and biomarker assays	Change in maximal descending thoracic aortic diameter and annualized growth rate Degree of false-lumen thrombosis Correlation between serum $\beta$ -hydroxybutyrate levels and aortic remodeling using finite-element imaging analysis Changes in systemic inflammatory and metabolic biomarkers Overall diet adherence and safety.

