# 6.0 Study Interventions

## 6.1 Study Procedures

Participants will initiate a supervised ketogenic diet formulated to provide approximately 70-75% of calories from fat, 20% from protein, and less than 10% from carbohydrates, consistent with protocols successfully used in therapeutic epilepsy trials but adapted for adult cardiovascular patients. Caloric intake will be individualized to maintain stable weight and adequate micronutrient balance. Each participant will receive an orientation session with a registered dietitian, followed by weekly virtual or phone check-ins for the first month and bi-weekly thereafter. Educational materials, individualized meal plans, and recipes will be provided.

To ensure safety and adherence, participants will use a handheld ketone meter (Keto-Mojo) to measure  $\beta$ -hydroxybutyrate levels three times per week via saliva as well as finger-stick blood testing. These readings will be automatically uploaded to a secure, HIPAA-compliant cloud platform monitored by the study team. Serum ketone validation and metabolic panels, including electrolytes, lipid profiles, and liver function tests, will be obtained at baseline and every three months. A study coordinator will review adherence data weekly and contact participants who fall below target ketosis thresholds ( $\geq 0.5 \text{ mmol/L}$ ). Blood pressure logs and medication compliance will be reviewed at each visit to ensure consistent impulse control (see

Table 1).

Imaging assessments will be performed using standard-of-care CTA at baseline, 6, and 12 months. All studies will follow an institutional low-radiation surveillance protocol optimized for chronic dissection. Measurements will include maximal descending thoracic diameter, true and false lumen cross-sectional areas, and extent of thrombosis. Each scan will be reviewed by two blinded imaging readers to minimize measurement bias.

Participants will remain under the care of their treating cardiovascular physicians throughout the study, ensuring continuation of best-practice medical management. Any indication for surgical or endovascular intervention during the trial will be determined by the treating team using standard clinical criteria, and the patient will be considered to have reached the primary study endpoint.

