## 6.2 Duration of Participation

The duration of active research participation is 12 months. Participants will remain under the care of their treating cardiovascular physicians throughout the study, ensuring continuation of best-practice medical management. Any indication for surgical or endovascular intervention during the trial will be determined by the treating team using standard clinical criteria, and the patient will be considered to have reached the primary study endpoint.

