### 7.1 Unanticipated Problems and Adverse Event Reporting

Adverse events will be tracked from the time of the baseline visit until the 12 Month visit. Only events that are considered at least possibly related to participation in this study will be recorded on the AE case report form.

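### Section 10 puts safety under intent-to-treat, so harm can be understated if anyone never starts the ketogenic diet or is followed after stopping it

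*Protocol*

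**What the plan says.** Section 10.0 sets one rule for the whole trial: "All analyses will follow an intent-to-treat principle". The Synopsis describes the study in the same terms, as a "prospective, single-arm, intent-to-treat pilot clinical trial". No exposed set is defined for safety.

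Safety belongs to the main question. The primary objective in section 3.0 is to "Test the feasibility, safety, and potential efficacy of inducing and maintaining nutritional ketosis". As an endpoint, safety appears only in the secondary list, as "Overall diet adherence and safety".

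On exposure and follow-up, section 6.1 says "Participants will initiate a supervised ketogenic diet", and section 6.2 says "The duration of active research participation is 12 months". Section 7.1 adds: "Adverse events will be tracked from the time of the baseline visit until the 12 Month visit". That window is not tied to time on the diet, although only events judged at least possibly related to participation are recorded.

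On summary measures, section 10.0 plans proportions with 95% confidence intervals for dichotomous outcomes. For continuous variables it plans means with standard deviations and repeated-measures mixed models.

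**The concern.** For efficacy, keeping everyone in the analysis is usually the cautious choice, because non-adherence pulls the estimate towards no benefit. For harm the same pull is in the reassuring direction. The stated question concerns the safety of being brought into ketosis and kept there, which is narrower than the safety of being offered a diet. With no randomised comparator, intent-to-treat preserves no balance between arms for safety. What it adds is people and visits without exposure.

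The second route matters more than it first appears, because many of the harms listed in section 2.3 are laboratory quantities (electrolytes, lipids, liver and kidney function, uric acid). Section 6.1 and Table 1 schedule repeated metabolic panels, lipids and weight, and section 10.0 would analyse these as continuous variables. Section 9.0 also makes certain harms a trigger for changing the diet, so exposure may be reduced most in those who tolerate it worst. At stake is whether a pilot that names safety in its primary objective reports a harm estimate that can be read as that of the diet.

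**Working it through.** The protocol gives no expected event rate or safety calculation, so there is no figure to reproduce. The figures below are illustrations.

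**1. Adverse-event proportion**

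Inputs: 15 enrolled (Synopsis: "15 patients- Prospective Cohort"). The number of non-starters, k, is an assumption, since the protocol gives none. Non-starters are assumed to have no recorded event, which is plausible because only possibly related events are recorded. A complication of a research blood draw would be an exception.

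Formula: x/15 under intent-to-treat and x/(15 − k) among those who start, with exact (Clopper-Pearson) 95% intervals.

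| Patients with an event (x) | k | All enrolled | Starters only |
|---|---|---|---|
| any | 0 | x/15 | x/15 (identical) |
| 2 | 1 | 2/15 = 13.3% (1.7 to 40.5) | 2/14 = 14.3% (1.8 to 42.8) |
| 2 | 3 | 2/15 = 13.3% (1.7 to 40.5) | 2/12 = 16.7% (2.1 to 48.4) |
| 3 | 2 | 3/15 = 20.0% (4.3 to 48.1) | 3/13 = 23.1% (5.0 to 53.8) |
| 0 | 3 | 0%, upper limit 21.8% | 0%, upper limit 26.5% |

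The shift is a few percentage points at most, well inside the sampling error.

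**2. Mean change in a continuous safety measure**

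Let d be the mean change on the diet, q the share of participants at a visit who have stopped the diet but still attend, and r the fraction of the change that persists after stopping. Take d to be the same in those who stop and those who continue. The pooled mean change is then

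(1 − q)·d + q·r·d = d·[1 − q(1 − r)].

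The protocol gives neither q nor r. Assuming 1 or 3 of 15 attenders are off diet:

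| q | r = 0 (full return to baseline) | r = 0.5 | r = 1 (no return) |
|---|---|---|---|
| 1/15 = 0.067 | 0.93 d | 0.97 d | d |
| 3/15 = 0.20 | 0.80 d | 0.90 d | d |

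The pooled mean equals the on-diet mean only if nobody is measured off diet (q = 0) or nothing reverts (r = 1). Otherwise it is smaller.

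**The case against.** **If all 15 start, the two sets are the same.** This is correct. Section 6.1 expects every participant to start, and section 4.2 excludes people unable to comply with dietary restrictions. The effect on the proportion is therefore conditional and small.

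**A reader might infer that event rates are diluted 1.4 to 1.8-fold.** The feasibility benchmarks of 80% retention and 70% adherence invite the product 0.80 × 0.70 = 0.56, hence 1/0.56 = 1.79, or 1/0.70 = 1.43 with full retention. The protocol does not support this. It plans proportions of participants, which have no month denominator, and no person-time rate. The product also mixes time in target ketosis with time on the diet: a participant eating the diet with a low ketone reading is still exposed to its risks. On-diet time alone would give at most 1/0.80 = 1.25, if drop-outs left at the start, and again only for a rate that is not planned.

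**A reader might also infer that people harmed early dilute the proportion by stopping.** They do not. A participant with an event in week 2 who then stops counts in full as one of 15, and an exposed set would keep the same person.

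**Safety sets are commonly left to the SAP, and the safety of assigning a diet is a legitimate question.** Both are fair. But the protocol does not leave the matter open. It fixes a rule for all analyses, and an SAP with an exposed safety set would depart from it. Intent-to-treat safety is reasonable as a supplementary summary, but it does not by itself answer the stated objective.

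**No safety decision rests on an aggregate rate.** This also stands: section 9.0 acts on individual events. The effect is on how the result is reported and read, and participant monitoring is unaffected.

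**Conclusion.** The point holds in a limited form. Section 10.0 places safety under intent-to-treat without exception, in a single-arm trial whose primary objective includes the safety of inducing and maintaining ketosis. The adverse-event proportion can be understated if someone never starts (20.0% versus 23.1% with 3 affected and an assumed 2 non-starters) and is unchanged if all start. Mean changes in laboratory safety values and weight can be understated where visits after stopping are pooled with on-diet visits. That size cannot be fixed from the protocol, because it depends on the number of off-diet visits and on how far values revert. Dilution is thus a possibility that the rule allows, not an established fact. Severity is minor, and the change is a cheap improvement.

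**What to change.** Limit the intent-to-treat sentence in section 10.0 to efficacy and feasibility, and add:

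*Safety is analysed in all participants who start the diet; adverse events and changes in safety laboratory values and weight are presented overall and by on-diet versus after-stopping status.*

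Record diet start and stop dates on the case report form. The home ketone readings and the scheduled visits already supply the rest, so no new visit or test is needed. An intent-to-treat safety summary may be kept as supplementary. The overall presentation should stay beside the split, because the participants still on the diet late in the year may be those who tolerate it best.

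The cost is an edit to section 10.0 and two dates per participant. The downsides are small subgroups in a 15-person trial, so the split is descriptive only, and a harm estimate that may look slightly less favourable.
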